7.5.4 Montreal Cognitive Assessment Test (MoCA)

The observed values and change from baseline values for MoCA total points and its subscale items (Attention, Language, Naming Visuospatial/Executive, Abstraction Points, Delayed Recall Points, and Orientation Points) by treatment group will be presented in a by-patient listing and in a summary table.

Differences in change from baseline of MoCA scores between Mirabegron and placebo will be analyzed using a stratified rank ANCOVA model. The response variable will be the change from baseline in MoCA scores. Treatment group and gender will be fixed factors in the model.. A subset analysis by age group (<75 , ≥ 75) will be included.. As part of the ANCOVA results, LS means, two-sided 95% CIs, and p-values for mean changes from baseline within each treatment group will be provided.

A simpler model will also be provided that includes only treatment, gender, and baseline MoCA values as covariates.

A shift table for MoCA total points by treatment group will be created by the following categories:

- >26: normal
- ≤ 26 : impaired
 - 18-26: mild cognitive impairment
 - 10-17: moderate cognitive impairment
 - <10: severe cognitive impairment.

The following MoCA data will be presented graphically by treatment group across visits:

- MoCA results using mean (+/- 95% CI) plot,
- Change from baseline in MoCA results using mean (+/- 95% CI) plot.

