7.4.4 Exploratory Analysis

7.5 Analysis of Safety

Safety analysis will be performed for adverse events (AEs) and vital signs using the SAF. No inferential comparison between treatment groups will be performed for the safety analysis in

this study with the exception of the change from baseline in Montreal Cognitive Assessment Test (MoCA) and for vital signs analysis.

Differences in change from baseline of MoCA scores between mirabegron and placebo will be analyzed using a stratified ANCOVA model. The response variable will be the change from baseline in MoCA scores. Treatment group and gender will be fixed factors in the model while the baseline symptom bother and total health related quality of life scores will be included as covariate. Age group (<75, \geq 75) will be included as the stratification factor. As part of the ANCOVA results, LS means and two-sided 95% CIs for mean changes from baseline within each treatment group will be provided.

Vital Signs will be summarized by treatment group and by Home Based Blood Pressure Monitoring (HBPM) versus office based using descriptive statistics for baseline value, specified post-baseline time point values (Week 4, Week 8, Week 12/EOT), and change from baseline to each specified post-baseline time points. Office based and morning and evening blood pressure will be reported separately. For HBPM the first reading from each time period will be discarded and the subsequent two readings for each time period will be averaged over the 3-day diary. HBPM and office based monitoring will be reported separately (See [Appendix 4](#)).

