7.1.2 Model Structure - Analysis of Covariance (ANCOVA)

Changes from baseline to a post-baseline visit for variables for which a normal distribution is assumed will be analyzed using the following ANCOVA model:

$$Ch_{i j k s} = \beta_0 + \beta_1 Base_{i j k s} + Trt_i + Gender_j + AgeGrp_k + \epsilon_{i j k s}$$

Where $Ch_{i j k s}$ is the change from baseline for subject s from treatment group i , gender group j , and age group k . β_0 and β_1 are the intercept and the slope of $Ch_{i j k s}$ as a function of the baseline value and $\epsilon_{i j k s}$ is the residual for each subject.

The ANCOVA model results will be presented with least squares (LS) means and two-sided 95% confidence intervals (CIs) for mean changes from baseline within each treatment group. Differences in LS means between Mirabegron versus placebo will be derived together with two-sided 95% CIs. T-statistics corresponding to the Type III sums of squares for the differences in the LS means will be used to obtain p-values for the comparisons. Distribution assumptions underlying the analysis will be assessed by residual plots.

The SAS code used to implement this test will be similar to that shown below:

```
PROC MIXED data=dataset COVTEST NOCLPRINT METHOD=ML;
  CLASS Trt Gender AgeGrp;
  MODEL Ch=Base Trt Gender AgeGrp / SOLUTION CLPARM;
  LSMEANS Trt / CL OM AT MEANS;
  ESTIMATE 'Mirabegron versus placebo Trt 1 -1 0 /est cl';
  RUN;
```

SAS code used to implement the rank ANCOVA will be similar to that shown below:

```
PROC RANK data=dataset NPLUS1 TIES=MEAN OUT=RANK1;
  VAR Base Ch ;
  RANKS BASERANK CHRANK ;
  BY AgeGrp ;
  RUN ;

PROC MIXED data=RANK1 METHOD=ML /RESIDUAL OUTP=OUT
  (KEEP=AgeGrp Gender CHRANK BASERANK Trt Resid);
  CLASS Gender ;
  BY AgeGrp ;
  MODEL CHRANK = BASERANK Gender ;
  RUN ;

PROC FREQ data= out ;
  TABLES AgeGrp*Trt*Resid /noprint CMH2 ;
  ODS OUTPUT CMH = out2 ;
  RUN ;
```

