H0: Mean change from baseline in number of incontinence episodes per 24 hours at end of treatment is the same for placebo and Mirabegron.

H1: Mean change from baseline in number of incontinence episodes per 24 hours at end of treatment is different for placebo and Mirabegron.

In order to test for statistical differences in Change from baseline to end of treatment in mean number of incontinence episodes per 24 hours between Mirabegron and placebo, a stratified rank ANCOVA will be used. The response variable is the standardized ranks of change from baseline to end of treatment value in mean number of incontinence episodes per 24 hours. Treatment group and gender will be added as fixed factors in the model while the standardized ranks of mean number of incontinence episodes per 24 hours at baseline will be included as a covariate. Age group (<75 , ≥ 75) will be included as the stratification factor. LS means and two-sided 95% CIs for mean changes from baseline within each treatment group will be provided using an ANCOVA model with the same dependent and independent variables but not using the rank scale for the mean number of incontinence episodes data.

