7.5 Analysis of Safety

Safety analysis will be performed for adverse events (AEs) and vital signs using the SAF. No inferential comparison between treatment groups will be performed for the safety analysis in this study with the exception of the change from baseline in Montreal Cognitive Assessment (MoCA).

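### The SAP's MoCA shift table counts a score of 26 as impaired, while the MoCA form in the SAP's own Appendix 5 counts 26 as normal.

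*SAP*

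**What the plan says.** SAP 7.5.4 defines the shift table in two layers. A total above 26 is normal and a total of 26 or less is impaired. Impaired is then split into "18-26: mild cognitive impairment", moderate at 10 to 17 and severe below 10.

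SAP 6.2 lists the MoCA as a safety variable and points to Appendix 5 for it. The form reproduced there prints one cut-off, under which 26 or more out of 30 is normal. It prints no bands below that. Protocol 5.4.3 gives the 30-point maximum and no categories.

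The inferential part of SAP 7.5.4 is separate. It names a stratified rank ANCOVA on change in MoCA score, promises LS means, 95% CIs and "p-values for mean changes from baseline within each treatment group will be provided", and adds: "A simpler model will also be provided that includes only treatment, gender, and baseline MoCA values as covariates". The rank ANCOVA code in SAP 7.1.2 fits "MODEL CHRANK = BASERANK Gender" within age group and passes the residuals to "TABLES AgeGrp*Trt*Resid /noprint CMH2".

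**The concern.** Two parts of the same SAP assign the same score to opposite sides of the normal/impaired line, and 7.5.4 gives no reason. Both layers of the 7.5.4 definition carry the same boundary, so a slip in one line does not explain it.

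A shift table is read mainly for movement across that line. Programmed as written, it would report subjects at 26 as cognitively impaired although the appended form calls them normal, and it would record shifts at that boundary differently from the form. The Introduction of the protocol presents this as the first mirabegron study to explore cognitive function in older patients. SAP 7.5 allows no inferential safety comparison "with the exception of the change from baseline in Montreal Cognitive Assessment". A table on this variable should agree with the instrument it summarises, or say why it does not.

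**Working it through.** **Comparing the rules.** The inputs are the 7.5.4 categories and the Appendix 5 cut-off. Each total from 0 to 30 was classified under both.

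| Total | SAP 7.5.4 | Appendix 5 form |
|---|---|---|
| 27 to 30 | normal | normal |
| 26 | impaired, mild | normal |
| 0 to 25 | impaired | below normal |

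One of the 31 possible totals changes side. The SAP has 4 normal scores and the form has 5. Of the 31 × 31 = 961 possible baseline and Week 12 pairs, 31 + 31 − 1 = 61 contain a 26, and those pairs are classified differently.

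- 27 to 26: SAP, normal to impaired; form, normal at both visits.
- 26 to 25: SAP, mild at both visits (no shift); form, normal to below normal.
- 26 to 26: no shift under either rule, but the cell moves from mild/mild to normal/normal.

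**How many subjects.** The documents give no MoCA mean, SD or between-visit correlation, so what follows rests on assumptions: a normal latent score with mean m of 22 to 26, SD s of 2.5 to 4.5, the same at both visits, and correlation r of 0.5 to 0.8. As a round denominator, 800 × (1 − 0.15) = 680 completers, using the planned drop-out.

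Exactly 26 at one visit: P = Φ((26.5 − m)/s) − Φ((25.5 − m)/s).

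- Lowest (m = 22, s = 2.5): Φ(1.8) − Φ(1.4) = 0.0448, and 0.0448 × 680 ≈ 30.
- Highest (m = 26, s = 2.5): Φ(0.2) − Φ(−0.2) = 0.1585, and 0.1585 × 680 ≈ 108. Truncating at 30 instead of capping gives 0.1585 / Φ(1.8) = 0.164.

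A 26 at baseline or Week 12: 2P − P(both 26), from the bivariate normal.

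- Lowest (m = 22, s = 2.5, r = 0.8): 2 × 0.0448 − 0.0100 ≈ 0.080, about 54 of 680.
- Highest (m = 26, s = 2.5, r = 0.5): 2 × 0.1585 − 0.0289 ≈ 0.288, about 196 of 680.

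Leaving out the 26-to-26 subjects, who show no shift under either rule: 2 × (P − P(both 26)), which gives about 7% to 26%.

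**Source of the promised estimates.** The 7.1.2 rank code ranks the data, regresses out ranked baseline and gender, and ends in a CMH test. It yields no treatment LS means or CIs. For incontinence, SAP 7.4.1 fills the same gap by taking within-group LS means and CIs from an ANCOVA with the same variables, "but not using the rank scale for the mean number of incontinence episodes data". SAP 7.5.4 has no such sentence.

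**The case against.** The case for leaving it alone is that the effect is small. The table is descriptive, MoCA is one safety variable under a secondary objective, and the same cut-off applies in both arms and at both visits. SAP 7.5.4 also plans a by-patient listing, summary statistics and change-from-baseline plots that use no cut-off, so a reader could re-cut the data. All of this stands and keeps the point minor, but it does not explain why the SAP contradicts its own appendix.

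An analyst may also choose a cut-off other than the printed one. The documents show an unexplained inconsistency, not proof that the form's value must govern the analysis. That is why a stated justification would be an acceptable fix.

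Some stronger readings go beyond the documents:

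- A reader might infer that the MoCA comparison between arms is distorted. It is not, because that analysis uses change in score and never the categories.
- A reader might infer that the form defines all four bands. It prints only the cut-off for normal; the lower bands are the SAP's own.
- A reader might infer that the MoCA test itself is undefined, because the protocol synopsis names a paired Wilcoxon test and Protocol 7.5 an ANCOVA in which "baseline symptom bother and total health related quality of life scores will be included as covariate". Protocol 7 leaves analysis detail to the SAP, and SAP 7.5.4 carries neither forward. The intended test can be recovered from the only rank ANCOVA code in the SAP. What is missing is the model behind the LS means and CIs.
- A reader might take 7.4.1 as precedent for a between-arm difference on the unranked scale for incontinence. In that paragraph the unranked model supplies within-group estimates only.

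**Conclusion.** The point holds, as a minor one. As written, the shift table in SAP 7.5.4 contradicts the form in Appendix 5 at a total of 26 and at no other score. The consequence is confined to that table. There is no effect on the MoCA test, and no bias between arms is claimed.

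The contradiction itself needs no assumption. The number of subjects involved is unknown. The range of roughly 8% to 29% with a 26 at either visit depends entirely on the assumed means, SDs, correlations and normal shape, and on the assumption that both visits share one distribution. The count of 680 is a planning figure for completers, whereas safety tables use the SAF. The range shows that the share need not be negligible, and it should not be quoted as an estimate for this trial.

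The missing source for the LS means is a gap in detail and secondary to the main point.

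**What to change.** Before database lock, move 26 into normal in the 7.5.4 categories: normal 26 or more, impaired below 26, mild 18 to 25. Keep the SAP's own 10 to 17 and below 10 bands. Alternatively, state in 7.5.4 why the table departs from the form.

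Optionally, add one sentence naming the unranked 7.1.2 ANCOVA with baseline MoCA as the source of the within-group LS means and 95% CIs, following the pattern of 7.4.1 for incontinence.

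The cost is one changed line, plus one sentence if the clarification is taken up. No new data are needed, since MoCA is already collected at Visits 3 and 6, and no other analysis changes.

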7.5.5 Electrocardiograms (ECGs)

ECG variables (heart rate, PR interval, RR interval, QRS interval, QT interval, and QTc interval) will be summarized using descriptive statistics and percentages for each treatment group at Baseline, Week 4, Week 8, and Week 12/End of Treatment, including changes from baseline to end of treatment.

Number and percent of subjects with normal, not clinically significant abnormal, and clinically significant abnormal results as assessed by investigator for the 12 lead ECG will be tabulated by treatment group at each treatment visit and time point.

Shift tables that include number and percent of subjects will be presented for 12 lead ECG reading changes from normal at baseline to abnormal at week 4, 8, 12, and EoT by treatment group.

The QTc interval will be summarized by gender using frequency tables for each treatment visit and time point for values of clinical importance using the range criteria below. It will also be summarized by FDA Guidance categories.

	QTc Interval Criteria Value (msec)
Gender Splits	≤ 450 for males, ≤ 470 for females - Normal > 450 for males, > 470 for females - Abnormal
FDA Categories	≤ 450 > 450 > 480 > 500

The QTc interval will also be summarized by the frequencies of subjects with a change from baseline of clinical importance using the criteria identified below. These summaries will be provided for each treatment visit and time point.

Variable	Change from Baseline
QTc Interval (msec)	<0 ≥ 0 >10 > 30 > 60

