7.5.5 Electrocardiograms (ECG)

ECG variables (heart rate, PR interval, RR interval, QRS interval, QT interval and QTc interval) will be summarized using frequency tables and percentages for each treatment group at Baseline, Week 4, Week 8, and Week 12/End of Treatment, including changes from baseline to end of treatment.

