Clarification of the determination of UTI and when urine cultures and sensitivity would be conducted.

RATIONALE:

Additional urinalysis criteria were necessary to trigger appropriate urine culture and sensitivity procedures.

5. Updated the definition of creatinine clearance (exclusion criteria #14).

DESCRIPTION OF CHANGE:

Clarified renal impairment is defined as estimated creatinine clearance (determined by Estimated Glomerular Filtration Rate [eGFR] or Cockcroft-Gault or MDRD formulae) less than 29 mL/min.

RATIONALE:

These statements were added to provide further clarification to the sites that a 24-hour urine was not required to measure creatinine clearance.

6. Edited QTcF to QTc (exclusion criteria #16).

DESCRIPTION OF CHANGE:

Removed the requirement to use QTcF to calculate QT prolongation (exclusion criteria #16).

RATIONALE:

Local ECG machines are used for the study and most sites were unable to provide the correction factor used on their machines. Some use Bazetts, not all sites will utilize the QTc corrected by the Fredericia method.

7. Removed exclusion criteria for completion of all 3-day micturition diaries.

DESCRIPTION OF CHANGE:

Exclusion criteria 3. Subject did not complete all 3 days of the 3-day micturition diary.

RATIONALE:

Subjects will be asked to complete 3-day micturition diaries, but the completion of all 3 days as an inclusion criterion will no longer be required. This will be consistent with other previous Astellas mirabegron clinical trials.

8. Updated Identification of Investigational Product(s)

DESCRIPTION OF CHANGE:

Manufacturing of test and placebo by Astellas Pharma Technologies, Inc. and packaging of aluminum blisters have been removed.

RATIONALE:

The information provided in the protocol is not correct- it had been carried over from another protocol. Astellas Pharma Technologies, Inc. is not manufacturing the test or placebo drugs.

In addition, the study product is only being provided in bottles and not with aluminum blisters. There is no change to the IP supply, just correction of the wording.

9. Updated Study Drug Handling

DESCRIPTION OF CHANGE:

The addition that any study drug handling procedures is authorized by Astellas.

RATIONALE:

This was an omission in the original protocol and provides additional clarification of the study drug handling.

10. Updated Prohibited Medications

DESCRIPTION OF CHANGE:

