7 STATISTICAL METHODOLOGY

7.1 General Considerations

In general, baseline is defined as the last measurement before the first dose of double-blind study drug. For variables based on the micturition diary, the 3 days of the diary recorded prior to the baseline visit will be used to derive these variables at baseline just as the 3 diary days before each post-baseline visit will be used to derive these variables at these visits.

The End of Treatment (EoT) visit is defined as the last post-baseline visit at the end of the double-blind treatment period for which data is available. The EoT visit value for diary variables is the average or number of the diary measurements for Week 12, as applicable. If no Week 12 diary data measurements are available, then the last available earlier post-baseline average or number of the diary measurements within a designated visit window will be used.

For continuous variables, descriptive statistics will include the number of subjects (n), mean, standard deviation, median, minimum and maximum. When needed, the use of other percentiles (e.g. 10%, 25%, 75% and 90%) will be mentioned in the relevant section.

Frequencies and percentages will be displayed for categorical data. Percentages by categories will be based on the number of subjects with no missing data, i.e. will add up to 100%.

All statistical comparisons will be made using a two-sided test at $\alpha = 0.05$ significance level and confidence intervals will be reported with a coverage consistent with this significance level.

A step-down gatekeeping procedure will be performed to control the type I error rate at the 0.05 significance level for the multiple endpoints of the co-primary efficacy variables of change from baseline to end of treatment in mean number of micturitions per 24 hours and mean number of incontinence episodes per 24 hours and the key secondary efficacy variable of change from baseline to end of treatment in mean volume voided per micturition. The hypotheses will be tested in the following order: mean number of micturitions per 24 hours, mean number of incontinence episodes per 24 hours and mean volume voided per micturition.

All data processing, summarization, and analyses will be performed using SAS[®] Version 9.3 or higher. Specifications for table, figures, and data listing formats can be found in the TLF specifications for this study.

For the definition of subgroups of interest please refer to [section 7.8](#).

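### SAP 7.5.5 counts subjects against fixed QTc limits without naming a heart-rate correction, although sites use local machines with mixed and mostly unknown corrections; deriving one QTcF from QT and RR would make the counts interpretable.

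*SAP*

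**What the plan says.** SAP 7.5.5 lists the ECG variables: "ECG variables (heart rate, PR interval, RR interval, QRS interval, QT interval, and QTc interval) will be summarized using descriptive statistics". For the threshold tables it adds: "The QTc interval will be summarized by gender using frequency tables for each treatment visit and time point for values of clinical importance". The limits are 450 msec for men and 470 msec for women, plus a second set at 450, 480 and 500 msec. For the change tables it says: "The QTc interval will also be summarized by the frequencies of subjects with a change from baseline of clinical importance", with cut-offs that include more than 10, 30 and 60 msec. Protocol 7.5.5 has the same variable list: "ECG variables (heart rate, PR interval, RR interval, QRS interval, QT interval and QTc interval) will be summarized using frequency tables and percentages". Neither section names a correction.

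The reason is in Protocol Attachment 1 (Substantial Amendment 2), non-substantial change 6, which replaced QTcF by QTc in exclusion criterion 16 and in Protocol 7.5.5. Its rationale reads: "Local ECG machines are used for the study and most sites were unable to provide the correction factor used on their machines". It continues: "Some use Bazetts, not all sites will utilize the QTc corrected by the Fredericia method". This explains the wording now in force; it is not superseded text. Protocol 5.4.7 has tracings read locally.

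SAP 7.1 sets the default display columns as placebo, mirabegron 25 mg (never titrated) and mirabegron 50 mg (titrated at week 4 or 8).

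**The concern.** A fixed limit has a definite meaning only if every value compared with it is on the same scale. Bazett and Fridericia agree at 60 bpm and diverge as heart rate moves away from it. If some sites report one, some the other, and most cannot say, then a count above 450 msec depends partly on which machines the subjects happened to attend, and it cannot be compared with other studies.

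Protocol 1.3.1 lists QT prolongation, with supratherapeutic doses or in high-risk populations, and increased heart rate among the important potential risks. The absolute QTc counts are therefore likely to be read for their own sake. What is at stake is how far those safety counts can be interpreted. No efficacy conclusion or planned test depends on them.

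**Working it through.** The plan states no figure to reproduce, so the check asks how far the two formulas differ at the SAP's own limits.

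**Inputs from the documents**
- Limits of 450, 470, 480 and 500 msec and change cut-offs of 10, 30 and 60 msec (SAP 7.5.5).
- Pulse change of about 1 bpm with mirabegron 50 mg (Protocol 1.3.1).

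**Assumed, not in the documents**
- Heart rate 50 to 90 bpm for the limits; for the change calculations, QTcF 400 to 440 msec and starting rate 60 to 80 bpm.

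**Formulas**, with RR = 60/HR in seconds
- Bazett: QTcB = QT/RR^(1/2). Fridericia: QTcF = QT/RR^(1/3).
- Hence QTcB/QTcF = (HR/60)^(1/6), which is 0.9701, 0.9856, 1, 1.0260, 1.0491 and 1.0699 at 50, 55, 60, 70, 80 and 90 bpm.

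**Step 1: QTcF equivalent of a Bazett reading exactly at each limit (msec)**

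| Bazett | 50 bpm | 55 | 60 | 70 | 80 | 90 |
|---|---|---|---|---|---|---|
| 450 | 463.9 | 456.6 | 450.0 | 438.6 | 428.9 | 420.6 |
| 470 | 484.5 | 476.9 | 470.0 | 458.1 | 448.0 | 439.3 |
| 480 | 494.8 | 487.0 | 480.0 | 467.8 | 457.5 | 448.6 |
| 500 | 515.4 | 507.3 | 500.0 | 487.3 | 476.6 | 467.3 |

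One tracing can fall on either side of a limit. With QT 390 msec at 80 bpm, RR = 0.75 s, so QTcB = 390/0.8660 = 450.3 (above 450) and QTcF = 390/0.9086 = 429.3 (below).

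**Step 2: the documented pulse change**
With QTcF held fixed, a rise of 1 bpm adds QTcF × {[(HR+1)/60]^(1/6) − (HR/60)^(1/6)} to the Bazett value. Over the assumed range this is 0.87 msec (QTcF 400, 80 bpm) to 1.21 msec (QTcF 440, 60 bpm). It arises only at Bazett sites, so the pooled shift is smaller. Protocol 1.3.1 also says that pulse increases were more pronounced in younger subjects, so it may be smaller still in a trial of people aged 65 and over.

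**Step 3: the change tables**
The QTcF change at which the Bazett change reaches each cut-off (range over the assumed values, msec):

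| Heart-rate change | >10 | >30 | >60 |
|---|---|---|---|
| +1 bpm (documented mean) | 8.6–8.9 | 27.6–28.8 | 56.2–58.7 |
| +8 bpm (assumed) | 0.7–3.1 | 20.3–21.8 | 49.4–50.5 |
| −8 bpm (assumed) | 16.8–20.9 | 36.2–41.3 | 65.3–72.1 |

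At the documented mean the distortion is small. A larger change within a subject distorts more, in either direction. For example, QTcF 420 to 442 with heart rate 70 to 78 is +22 by Fridericia and 461.8 − 430.9 = +30.8 (before rounding) by Bazett. The documents give no within-subject heart-rate variability, so the 8 bpm rows are illustrations only.

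**Step 4: which comparisons randomisation protects**
Allocation is 1:1, so the mix of formulas is balanced in expectation between all mirabegron and placebo. The 25 mg and 50 mg columns are formed by titration after randomisation, on efficacy, tolerability and investigator discretion. Randomisation gives no such balance there.

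**The case against.** **The choice was deliberate.** Change 6 moved Protocol 7.5.5 from QTcF to QTc because sites could not supply the correction, so the analysed variable is most naturally the site-reported value. This stands, and the point is therefore not that the variable is a mystery. Yet the amendment settles what sites can report, not what can be calculated from QT and RR, which remain listed analysis variables.

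**A derivation may exist elsewhere.** SAP 7.1 says: "Specifications for table, figures, and data listing formats can be found in the TLF specifications for this study". Those specifications are not available here and are described as covering formats. If they hold a derivation, SAP 7.5.5 need only state it.

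**The stakes are low and other safeguards exist.** SAP 7.5 plans no between-group ECG test. SAP 7.5.5 also tabulates heart rate, RR and uncorrected QT, and "Number and percent of subjects with normal, not clinically significant abnormal, and clinically significant abnormal results as assessed by investigator". Clinically significant abnormalities become adverse events (Protocol 5.4.7), serious arrhythmias are summarised (SAP 7.5.1), and serious cardiovascular events go to blinded adjudication (Protocol 10.2.1). All this stands and limits the severity, although none of it puts QTc on one formula.

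**Two stronger readings are not supported.** A reader might infer that the mixed formulas bias the comparison of mirabegron with placebo. The formula mix itself is balanced in expectation, and the remaining rate-dependent shift is about 1 msec at Bazett sites. A reader might equally infer that randomisation removes every between-column problem. It does not, because of that shift and because the default dose columns are not randomised groups. Nor can anyone say from the documents how many subjects would be misclassified; any such count needs assumed QTc and heart-rate distributions.

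**Conclusion.** The concern holds as a minor, inexpensive improvement. As written, the plan pools QTc values on different and mostly unknown corrections against single limits, so the threshold and change counts cannot be read in absolute terms. At a Bazett site the 450 msec limit corresponds to a QTcF between 456.6 msec at 55 bpm and 428.9 msec at 80 bpm.

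For all mirabegron against placebo, the expected distortion is confined to a possible shift of about 0.9 to 1.2 msec at Bazett sites if the 1 bpm pulse change is a drug effect. For the 25 mg and 50 mg columns no balance of formulas can be assumed. The conclusion rests on site-reported QTc being the analysed value and on no derivation existing in an unseen document. The sizes rest on the assumed QTcF and heart-rate ranges.

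**What to change.** In SAP 7.5.5:
- Derive QTcF = QT/(RR in seconds)^(1/3) for every ECG from the recorded QT and RR, with RR = 60/heart rate where RR is missing.
- Use it for the main QTc summaries, the sex-specific and 450/480/500 categories, and the change categories.
- Show these for all mirabegron against placebo as well as in the SAP 7.1 default columns.
- Report the number of ECGs for which QTcF cannot be derived.
- Keep site-reported QTc as a supplementary summary, with a footnote that entry used site QTc.
- If a derivation already exists elsewhere, state it here.

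The cost is one derived variable and an extra set of tables. It depends on numeric QT and RR or heart rate being recorded, which the variable list implies but no eCRF page confirms. Baseline QTcF may not match the QTc used at entry: a man admitted at a Bazett 450 msec with a heart rate of 55 bpm would show 456.6 msec. One formula does not remove differences between machines, readers or sitting and supine recordings. Eligibility and clinical rules stay as they are.
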